11.1.4 Seriousness

Each adverse event is to be classified by the investigator as SERIOUS (including life-threatening) or NON-SERIOUS. This classification of the gravity of the event determines the reporting procedures to be followed.

An adverse event that meets one or more of the following criteria/outcomes is classified as SERIOUS:

- Death
- Life-threatening (*i.e.*, immediate risk of death)
- Inpatient hospitalization or prolongation of existing hospitalization
- Persistent or significant disability/incapacity
- Congenital anomaly/birth defect in the offspring of a subject
- An event not included in the list above, but one that jeopardizes the subject or may require intervention to prevent one of the outcome listed above

A NON-SERIOUS event is one that does not meet the criteria described for a serious or life-threatening event.

11.2 Evaluation of Adverse Events

The Common Terminology Criteria for Adverse Events (CTCAE version 4.0) (http://ctep.cancer.gov/protocoldevelopment/electronic_applications/docs/ctcaev4.pdf) will be used to grade the maximum intensity of the event.

The acute toxicity assessment will be performed 1 month after the last radiosphere treatment. The patient will be re-evaluated for late toxicity at 3-month follow-up visit. After completion of the 3-month visit, patients will be followed every three months for 2 years for survival. Follow-up over the telephone will be allowed for this purpose. During this follow-up period, if investigators consider that patients develop a serious adverse event that would be possibly related to the study treatment, such SAE will be reported.

11.3 Attribution of Causality of Adverse Events

One of the investigators will assign an attribution to each AE that occurs. Attribution will be determined according to the criteria specified in CTCAE v4.0, which are summarized below:

5-Definite – The AE is *clearly related* to the treatment.

4-Probable – The AE is *likely related* to the treatment.

3-Possible – The AE *may be related* to the treatment.

2-Unlikely – The AE is *doubtfully related* to the treatment.

1-Unrelated – The AE is *clearly not related* to the treatment.

11.4 Reporting Adverse Events

Any adverse event that is associated with treatment and that is both serious and unexpected will be reported to FDA by telephone or FAX within 7 days. All of the investigators and the Thomas Jefferson University IRB will be notified as well. A follow-up safety report will be submitted within 15 days of initial notification.

In addition, the Sirtex Medical Inc. is to be notified within 24 hours of becoming aware of any serious adverse event.

Medical Director

Sirtex Technology Pty. Ltd.

Email: [contact]

[contact]

AE's will be reported to the Thomas Jefferson University IRB and the Clinical Research Management Office (CRMO) as specified in the TJU Data Safety and Monitoring Plan.

Unexpected fatal adverse events associated with treatment will be reported within 24 hours to the TJU IRB, to the Data Safety Management Board (DSMB) and to Sirtex.

Fatal adverse events not related to treatment will be reported to the TJU IRB and to the DSMB within 5 days.

AE will be reported according the table below.

Unexpected Event		
Grade 1-3 Attribution of Possible, Probable or Definite	Grade 4 Regardless of Attribution	Grade 5 Death
Report to CRMO via website within 48 hours. Report to TJU IRB within 48 hours. CRMO reports to DSMB immediately following receipt.	Report to CRMO via website and TJU IRB within 48 hours. CRMO reports to DSMB immediately following receipt.	Report to CRMO via website and TJU IRB within 24 hours. Report to Sirtex within 24 hours.

Expected Event		
Grades 1-3	Grade 4 Regardless of Attribution	Grade 5 Death
Report to CRMO via website within 10 working days. Summary of all adverse events submitted quarterly to DSMB.	Report to CRMO via website and TJU IRB within 48 hours. CRMO reports to DSMB immediately following receipt. Summary of all adverse events submitted quarterly to DSMB.	Report to CRMO via website and TJU IRB within 24 hours. Summary of all adverse events submitted quarterly to DSMB.

11.5 Thomas Jefferson University Data and Safety Monitoring Plan

The study will be conducted in accordance with the Thomas Jefferson University Data and Safety Monitoring Plan. Adverse events will be recorded and graded based on CTCAE v4.0. All adverse events will be reported to the Kimmel Cancer Center Clinical Research Management Office (CRMO) using a password-protected web-site. **Unexpected fatal adverse events associated with radiosphere treatment will be reported within 24 hours to**

the TJU IRB. Fatal adverse events not related to radiosphere treatment will be reported to the TJU IRB and to the DSMB within 5 days. None-fatal events will be reported according to the table in Section 11.4.

11.6 Follow-Up of Adverse Event

All AE's will be followed until they are resolved or the subject's participation in the trials ends. In addition, all SAE's will be followed by one of the investigators at Thomas Jefferson University even after the subject's participation in the trial is completed until they resolve or until one of the investigators assesses them as "chronic" or stable".

12.0 Statistical Considerations

This is a phase II clinical trial to investigate safety and efficacy of radioactive microsphere (*SIR-Spheres® microspheres*). Uveal melanoma patients with progressing hepatic metastases who received no more than one intra-hepatic arterial treatment will be enrolled. Patients will be first stratified into two groups: Group A, no prior intra-hepatic arterial treatment; Group B, one prior intra-hepatic arterial treatment).

A total of 24 uveal melanoma patients will be enrolled into each group. The primary endpoint of this study is the clinical benefit rate (CR+PR+SD). A Simon's two-stage optimal design (alpha=0.05, beta=0.20) will be applied to each group of patients (42, 43). The 60% of clinical benefit rate will be considered effective enough for the future investigation of this treatment. The radiosphere treatment will be considered to be ineffective if clinical benefit rate is 30% or less.

Choice of design is guided by a desire to stop the trial early if the actual stabilization rate is 30% or less. If the stabilization rate is 60% or greater, we would like to have a low probability of failing to conclude effective. Based on the optimal design, we will:

	Look after this number of patients	Stop if number of successes is less than or equal to
Stage I:	8	3
Stage II:	24	10

With this design, we have no more than a 5% chance of concluding effective ($\geq 60\%$ success rate) when the success rate is at most 30%. Similarly, we have no more than a 20% chance of concluding ineffective ($\leq 30\%$ stabilization rate) when it is effective. If the actual response rate is 30% or worse, we have at least a 0.81 probability that the trial will stop after the first 8 subjects. If the response rate is $\geq 60\%$, the probability that the trial will be stopped in stage I is 0.17. The overall power of this design is 80.6%.

The first stage of study requires 8 patients in each cohort. If 3 or fewer patients achieve stabilization or regression of hepatic metastases, further enrollment of patients into that group will be stopped with the conclusion that clinical benefit rate can not be 60% or greater. If at least 4 patients show response (CR, PR, or SD) in at least one of these two groups, the study will be continued to accrue 16 more patients in that group(s). If 10 or fewer patients among 24 patients in the group(s) show stabilization or regression of hepatic metastases, the study will be concluded that clinical benefit rate will not be 60% or more and no further study will be considered for the patients from the corresponding group(s).

We are currently treating 50-100 new uveal melanoma patients with hepatic metastases at Thomas Jefferson University Hospital. Approximately 1-2 patients would be accrued to this study every months and the accrual to this study will be completed within 2 years.

The estimated median survival of patients who receive this treatment is 6-12 months. We will follow the patients until their death or for 2 years. A maximum of 4 years including accrual of patients will be required to complete this study.

The overall survival (OS), progression free survival without progression of hepatic metastasis (PFS-L), and duration of response will be evaluated using the Kaplan-Meier method. All estimates of rates (e.g., clinical benefit rate and toxicity) will be presented with corresponding confidence intervals. For clinical benefit rates, the method of Atkinson and Brown will be used to adjust for the two-stage design (44).

All molecular and immunological studies are exploratory and the results will be reported in a descriptive manner. The genome-wide SNP analysis will be done at the KCC core facility. Paired

t-test or paired Wilcoxon test will be used to compare the serum cytokines and T cell subpopulations before and after radiosphere treatment.

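### Section 12.0 words a failed Simon boundary as showing that the clinical benefit rate is below 60%, which the two-stage design does not support

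*Combined protocol and SAP*

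**What the plan says.** All of this is in the combined protocol and SAP, section 12.0 Statistical Considerations.

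- Design: "A Simon's two-stage optimal design (alpha=0.05, beta=0.20) will be applied to each group of patients". The rate of interest is 60%. For the other end, "The radiosphere treatment will be considered to be ineffective if clinical benefit rate is 30% or less".
- Boundaries per group: stop at 3 or fewer successes in 8; negative at 10 or fewer in 24.
- Error rates: for an effective treatment, "we have no more than a 20% chance of concluding ineffective", and at a rate of 60% or more, "the probability that the trial will be stopped in stage I is 0.17". When the section describes these errors it attaches a rate of at least 60% to an effective conclusion and a rate of at most 30% to an ineffective one.
- Prescribed stage I conclusion: "further enrollment of patients into that group will be stopped with the conclusion that clinical benefit rate can not be 60% or greater".
- Prescribed stage II conclusion: "the study will be concluded that clinical benefit rate will not be 60% or more", with no further study in that group.
- Reporting: rates "will be presented with corresponding confidence intervals", and for the clinical benefit rate "the method of Atkinson and Brown will be used to adjust for the two-stage design". No confidence level is given.

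**The concern.** The boundaries are set so that crossing them rejects 30%. Failing to cross them leaves 30% unrejected; it does not reject 60%. The section nevertheless prescribes, for the primary endpoint, a finding about 60%, and at stage I it does so on eight patients and in the language of impossibility.

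What is at stake is the report. A group that stops at 3 of 8 would be described as having a rate below 60%, next to a planned confidence interval that can extend well above 60%. The section also describes a negative result in two ways, as a rate of at most 30% and as a rate below 60%. The test supports neither as a conclusion.

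**Working it through.** **Inputs (section 12.0).** Null rate 0.30; target rate 0.60; stage I n = 8, stop at ≤ 3; total n = 24 (16 more patients), negative at ≤ 10. Write b(x; n, p) for the binomial probability.

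**1. The plan's own figures.**

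Early stop = Σ b(x; 8, p) over x = 0 to 3.

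- p = 0.30: 0.0576 + 0.1977 + 0.2965 + 0.2541 = 0.8059 (plan: 0.81).
- p = 0.60: 0.0007 + 0.0079 + 0.0413 + 0.1239 = 0.1737 (plan: 0.17).

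P(declared effective) = Σ b(x; 8, p) × P(X₂ ≥ 11 − x | 16, p) over x = 4 to 8.

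- p = 0.30: 0.0462 (plan: no more than 5%).
- p = 0.60: 0.8063 (plan: 80.6%).

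A search over designs returns 3/8 and 10/24 as the optimal design. The stated design is correct.

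**2. How often a true 60% gives a negative result.** 1 − 0.8063 = 0.1937, made up of 0.1737 at stage I and 0.0200 at stage II. Among groups that continue, the stage II failure rate is 0.0200 / (1 − 0.1737) = 2.4%. The overstatement is therefore mainly a stage I matter.

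**3. Does the interval exclude 60%?** An exact upper limit lies below 60% only if P(a result as low or lower | p = 0.60) is under α/2, which is 0.025 for a 95% interval and 0.05 for a 90% interval. The documents do not describe how the cited method orders results across stages. Three orderings were therefore tried as assumed stand-ins: by stage, by observed rate and by total count. For the results below, all three give the same upper limits to the precision shown.

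| Result | P(as low or lower at 60%) | Upper limit, 95% | Upper limit, 90% | 60% inside? |
|---|---|---|---|---|
| 0/8 | 0.0007 | 36.9% | 31.2% | no |
| 1/8 | 0.0085 | 52.7% | 47.1% | no |
| 2/8 | 0.0498 | 65.1% | 59.97% | at 95% only |
| 3/8 | 0.1737 to 0.1797 | 75.5% | 71.1% | yes |
| 9/24 | 0.1797 | 75.5% | 71.1% | yes |
| 10/24 | 0.1937 | 75.6% | 71.2% | yes |

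Unadjusted Clopper-Pearson upper limits, for comparison: 10/24 gives 63.4% (95%) and 60.3% (90%), both still above 60%. 9/24 gives 59.4% (95%), so at 9/24 the answer depends on the method.

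**4. Share of negative results at a true 60% whose adjusted interval includes 60%.**

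- 95% level: 0/8 and 1/8 exclude it. 1 − 0.0085 / 0.1937 = 95.6%.
- 90% level: 0/8, 1/8 and 2/8 exclude it. 1 − 0.0498 / 0.1937 = 74.3%.

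Results of 8 or fewer in 24 depend on the ordering, but their total probability is only 0.1751 − 0.1737 = 0.0014. They could move either share by at most 0.0014 / 0.1937 = 0.7 percentage points.

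**The case against.** The strongest reply is that this is ordinary phase II shorthand. The error rates stand just before the disputed sentences, and there the word for concluding names a test decision with a known chance of being wrong. A reader of the whole section is unlikely to think that 60% has been excluded with certainty. Every action also hangs on the count rule alone, while the interval is only a presentation of the estimate. So the plan leaves no doubt about what to do, only about how a report should word the two results together.

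Much of this stands. It is why the point is minor, and why the 60% and 30% labels in the error-rate sentences may fairly be read as design hypotheses. It does not rescue the stage I and stage II sentences, which instruct what is to be concluded about the rate. Disclosing a 0.17 chance of a stage I stop at 60% shows the conflict; it does not remove it.

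A reader might infer three stronger things that the documents do not support:

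- That the design or stopping rule is faulty. The stated operating characteristics all reproduce.
- That every negative result would sit beside an interval containing 60%. It would not at 0/8 or 1/8, nor at 2/8 with a 90% level, and 9/24 depends on the method.
- That about 96% is the single share of affected negative results. That figure assumes a 95% level, which the plan does not state; at 90% it is about 74%.

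**Conclusion.** The concern holds for the wording of the negative conclusions only. A group with a true 60% rate would receive the prescribed conclusion 19.4% of the time. At both boundaries the adjusted interval includes 60% at the 95% and 90% levels under every ordering tried. Across all negative results at a true 60%, between about 74% (90% level) and 96% (95% level) would carry an adjusted interval that includes 60%.

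The 19.4% rests only on the plan's own design. The interval figures rest on two assumptions: the confidence level, which is not stated, and the orderings, none of which is claimed to be the cited Atkinson and Brown method.

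Boundaries, sample size, alpha (0.046), power (80.6%) and the decision not to pursue a failing group are sound. Severity is minor, because no stopping or go/no-go decision changes.

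**What to change.** In section 12.0:

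- Replace both prescribed negative conclusions (3 or fewer of 8; 10 or fewer of 24) with: *not shown to exceed 30%; criterion for further study not met in this group*.
- Add that 60% is to be described as excluded only if the planned two-stage-adjusted interval excludes it.
- Where the error rates are described, mark the rates of at least 60% and at most 30% as the design hypotheses, not as conclusions.

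The cost is a few sentences. Boundaries, sample size, error rates and analysis method stay as they are. The downside is that the negative conclusion the report may state becomes more modest.

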7.5 Immunological and cytokine response to radiosphere treatment

It has been reported that local liver treatments induce inflammatory cytokines and also change the levels of angiogenic cytokines (39)(40), which might contribute to a clinical response to the treatment. We have also reported that a pattern of productions of IL-6, IL-8, and TNF-alpha is different between uveal melanoma patients who received immunoembolization with GM-CSF for their hepatic metastases and those treated with plain embolization without GM-CSF (41). It is speculated that radiation treatment to established tumors would result in destruction of tumor-induce immunosuppressive microenvironment and might induce an anti-tumor immune response. To investigate this hypothesis, blood specimens will be collected prior to, and after radiosphere treatments and changes in serum cytokines and T cell subpopulation including regulatory T cells and memory T cells will be investigated. We hypothesized that patients with a good clinical response have decrease in circulating regulatory T cells and increase in a subset of memory T cells as seen in immunoembolization studies (unpublished data).

Approximately 100ml of blood specimens will be obtained for PBMC collection prior to radiosphere treatment and then at 1-month and 3-month office visits. Additionally, 10 ml of blood specimens will be obtained for serum collection prior to, and 1 hour after radiosphere treatment, and then at 1-month and 3-month office visits.

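### The before/after tests of T-cell change leave clinical response out, so they cannot tell a response-linked change from a general treatment effect

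*Combined protocol and SAP*

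**What the plan says.** Section 7.5 first speculates that irradiating tumours may undo local immunosuppression and provoke an immune response, and has blood drawn before and after treatment to look for changes in cytokines and T-cell subsets. It then adds a hypothesis tied to outcome: "We hypothesized that patients with a good clinical response have decrease in circulating regulatory T cells and increase in a subset of memory T cells". T cells are sampled by "PBMC collection prior to radiosphere treatment and then at 1-month and 3-month office visits".

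Section 12.0 names one method for these data, a paired "t-test or paired Wilcoxon test will be used to compare the serum cytokines and T cell subpopulations before and after radiosphere treatment". It mentions no responder subgroup, no comparison of change by outcome, and no correlation or regression on response. It does not say which post-treatment sample is meant. It also sets the status of the work: "All molecular and immunological studies are exploratory and the results will be reported in a descriptive manner".

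Good clinical response is not defined for this hypothesis. Elsewhere Section 12.0 counts CR, PR and SD together: "If at least 4 patients show response (CR, PR, or SD) in at least one of these two groups".

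**The concern.** The second hypothesis in Section 7.5 concerns patients who do well. The named test asks whether the mean change is zero and, as written, takes no account of who did well. A fall in regulatory T cells common to everyone after liver irradiation would give a significant paired test with no relation to response.

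What is at stake is interpretation. Section 7.5 suggests that immune changes might contribute to clinical response, so a significant before/after result could be read as support for that idea without having tested it. Patients give about 100 ml of blood at each of three times, and the comparison that bears on the hypothesis is not in the plan.

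**Working it through.** **The plan's own figures.** The only powered analysis is the primary one: "A Simon's two-stage optimal design (alpha=0.05, beta=0.20) will be applied to each group of patients". With stopping bounds 3/8 and 10/24, exact binomial calculation gives stage I stopping probabilities of 0.806 at a 30% rate (stated 0.81) and 0.174 at 60% (stated 0.17), type I error 0.046 (stated at most 5%) and power 0.806 (stated 80.6%). All reproduce. None concerns T cells, for which the documents give no effect size, SD or power.

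**Inputs.** n=24 is one full group ("A total of 24 uveal melanoma patients will be enrolled into each group"); n=48 is both groups if both complete stage II. Success shares of 30% and 60% are the design's two rates; 50% is an added case. Effects are assumed, in units of the SD of within-patient change. Tests are two-sided at 5%.

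**What each test targets.** Let a share π of patients respond, with mean change δR in responders and δN in the others.

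- Pooled paired test: πδR + (1-π)δN.
- Comparison by outcome: δR - δN.

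Either can be zero while the other is not.

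**Case 1: everyone changes by -0.5, no link to response.** The paired test has noncentrality 0.5√n.

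- n=24: 0.5 × √24 = 2.449, critical t 2.069 on 23 df, rejection 65%.
- n=48: 0.5 × √48 = 3.464, critical t 2.012 on 47 df, rejection 92% (simulations gave 91% to 93%).
- By outcome, δR - δN = 0, so rejection stays near 5% (rank-sum simulations 4% to 5%).

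**Case 2: only responders change.** This is closest to the sentence in Section 7.5. The pooled signal is about πδR√n and the between-group signal δR√(nπ(1-π)), so their ratio is about √(π/(1-π)): 1.00 at 50%, √1.5 = 1.22 at 60%, and √(0.3/0.7) = 0.65 at 30%. Simulated rejection rates agree:

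| Successes, responder change | n | Pooled paired | By outcome | Paired, responders only |
|---|---|---|---|---|
| 50%, -0.5 | 24 | 20% | 19% | 35% |
| 50%, -0.5 | 48 | 37% | 39% | 65% |
| 60%, -0.5 | 24 | 25% | 20% | 41% |
| 60%, -0.5 | 48 | 51% | 36% | 73% |
| 30%, -0.8 | 24 | 16% | 40% | 43% |
| 30%, -0.8 | 48 | 31% | 70% | 80% |

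The by-outcome test is rank-sum in the first four rows and a two-sample t-test in the last two. The pooled test falls clearly behind only when successes are few.

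**Paired test in responders only.** This addresses the literal sentence in Section 7.5, but under Case 1 with half successes it still rejects in about 36% (n=24) and 64% (n=48) of trials. Alone, it does not show that the change is specific to responders.

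**Precision of a comparison by outcome.** The difference detectable with 80% power is about (1.960 + 0.842) × √(1/k + 1/(n-k)), with k = nπ.

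- n=24: 1.17 SD at 60% successes, 1.25 SD at 30%.
- n=48: 0.83 SD at 60%, 0.88 SD at 30%.
- A group stopped at 8 has at most 3 successes: 2.802 × √(1/3 + 1/5) = 2.05 SD, and the normal approximation is optimistic at that size.

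**The case against.** The strongest reply is that the paired test fits the question to which Section 7.5 ties the blood sampling, namely whether cytokines and T cells change after treatment. That stands. The responder sentence is an added hypothesis and covers T cells only. Section 12.0 also does not forbid analysis by response category, and a paired test within responders would address the literal sentence. That stands too, but the restriction is not written down, and it would not separate a responder effect from a shared one.

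The analyses are exploratory and to be reported descriptively, and immunology is not among the objectives or endpoints in Section 2. This limits the weight of the point. It does not remove it, since the plan still names significance tests and a directional hypothesis.

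A reader might go further and infer that the paired tests are the wrong kind of test, or that a real association would usually be missed. The documents do not support this. A striking contrast can be built: with half successes, responders at -0.5 and the others at +0.5, the paired test rejects in 2% to 3% of trials at n=48 against about 90% for a rank-sum test. But nothing in the documents predicts an opposite change in non-responders.

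**Conclusion.** The point holds as a minor gap between a stated hypothesis and the analysis named for it. The paired tests answer the first question in Section 7.5. As written they do not answer the second, because response is not in them. The issue is what a rejection means: an assumed shared change of -0.5 SD unrelated to response is declared significant in about 65% (n=24) to 92% or 93% (n=48) of trials, against about 5% by outcome. The size depends on the assumed effect; the logic does not.

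Power is secondary. If only responders change, the tests are about equal at 50% successes, the pooled test does somewhat better at 60%, and it does worse at 30%. The primary endpoint, sample size and stopping rules are unaffected.

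**What to change.** In Section 12.0:

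- Keep the paired tests as the analysis of overall change, and name the post-treatment sample each one uses.
- State in advance which response categories count as a good clinical response.
- Add an exploratory comparison of within-patient T-cell change, from baseline to 1 month and to 3 months, between patients with and without clinical benefit (CR+PR+SD), by rank-sum test or baseline-adjusted regression. Report estimates with confidence intervals, alongside the paired change within responders.
- Say that a before/after change alone will not be taken as evidence of a link to response.

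The cost is a few lines of text and analysis, since samples and response are already collected. The downsides should be named:

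- Precision is low, especially if a group stops at 8 patients.
- Two time points and several T-cell subsets add unadjusted comparisons.
- Progression is a withdrawal criterion (Section 5.9), so 3-month samples may be lost selectively among patients who progress. Sample counts by outcome and visit should be reported.
- Section 7.1.4 classes unconfirmed SD as PD, so the group without benefit may include patients who only lacked a confirming scan.
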